## 7.2 Monitoring for Adverse Events

At each visit, after the subject has had the opportunity to spontaneously mention any problems, the Investigator should inquire about AEs by asking the standard questions:

- “Have you had any health problems since your last study visit?”
- “Have there been any changes in the medicines you take since your last study visit?”

Additionally, changes in *any protocol-specific parameters and/or questionnaires* evaluated during the study are to be reviewed by the Investigator. Any untoward (unfavorable and unintended) change in *a protocol-specific parameter or questionnaire response* that is clinically relevant, in the opinion of the Investigator, is to be reported as an AE. These clinically relevant changes will be reported regardless of causality.

## 7.3 Procedures for Recording and Reporting

AEs are collected from the time of informed consent. Any pre-existing medical conditions or signs/symptoms present in a subject prior to the start of the study (ie, before informed consent is signed) are not considered AEs in the study and should be recorded in the Medical History section of the eCRF.

In addition, temporary lens awareness or visual changes during the fitting process are not considered AEs if the Investigator assesses that the symptom(s) can reasonably resolve within the anticipated adaptation period.

- ADEs or SAEs are documented on the *Serious Adverse Event and Adverse Device Effect* eCRF within 24 hours of the Investigator’s or site’s awareness.
- Device deficiencies are documented on the *Device Deficiency* eCRF within 24 hours of the Investigator’s or site’s awareness.

- A printed copy of the completed *Serious Adverse Event and Adverse Device Effect* and/or *Device Deficiency* eCRF must be included with product returns.
- Additional relevant information after initial reporting must be entered into the eCRF as soon as the data become available.
- Document any changes to concomitant medications on the appropriate eCRFs.
- Document all relevant information from Discharge Summary, Autopsy Report,
- Certificate of Death, etc, if applicable, in narrative section of the *Serious Adverse Event and Adverse Device Effect* eCRF.

*Note:* Should the EDC system become non-operational, the site must complete the appropriate paper *Serious Adverse Event and Adverse Device Effect* and/or *Device Deficiency* Form. The completed form is emailed to the Study Sponsor at [[contact]](mailto:[contact]) according to the timelines outlined above; however, the reported information must be entered into the EDC system once it becomes operational.

Any AEs and device deficiencies for non-study marketed devices/products (ie, RepleniSH) will be considered and processed as spontaneous (following the postmarket vigilance procedures) and should be communicated to the device's/product's manufacturer as per local requirements.

Study Sponsor representatives may be contacted for any protocol related question.

Further, depending upon the nature of the AE or device deficiency being reported, the Study Sponsor may request copies of applicable portions of the subject's medical records. The Investigator must also report all AEs and device deficiencies that could have led to a SADE according to the requirements of regulatory authorities or IRB/IEC.

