
Exclusion Criteria
	
 
1. Any anterior segment infection, inflammation, or abnormality or disease (including systemic) that contraindicates contact lens wear, as determined by the Investigator.
 
2. Any use of systemic or ocular medications for which contact lens wear could be contraindicated, as determined by the Investigator.
 
3. History of refractive surgery or plan to have refractive surgery during the study or irregular cornea in either eye.
 
4. Ocular or intraocular surgery (excluding placement of punctal plugs) within the previous 12 months or planned during the study.
 
5. Biomicroscopy findings at screening that are moderate (Grade 3) or higher and/or corneal vascularization that is mild (Grade 2) or higher; presence of corneal infiltrates.
 
6. Current or history of pathologically dry eye in either eye that, in the opinion of the Investigator, would preclude contact lens wear.
 
7. Current or history of herpetic keratitis in either eye.
 
8. Eye injury in either eye within 12 weeks immediately prior to enrollment for this trial.
 
9. Current or history of intolerance, hypersensitivity or allergy to any component of the study products.
 
10. Wearing habitual contact lenses in an extended wear modality (routinely sleeping in lenses for at least 1 night per week) over the last 3 months prior to enrollment.
 
11. Any use of topical ocular medications, artificial tear or rewetting drops that would require instillation during contact lens wear.
 
12. The Investigator, his/her staff, family members of the Investigator, family members of the Investigator’s staff, or individuals living in the households of the aforementioned persons may not participate in the study.
 
13. Participation of the subject in a clinical trial within the previous 7 days or currently enrolled in any clinical trial.
 

	14. Habitual Biofinity contact lens wearers. 15. Monovision contact lens wearers.
Associated Materials	

• OPTI-FREE® RepleniSH® multi-purpose disinfection solution (RepleniSH)

• Lubrication/rewetting drops will not be permitted during lens wear. However, habitual lubrication/rewetting drop usage is allowed up to 10 minutes prior to lens insertion and any time after lens removal. No lubrication/rewetting drop use will be allowed during clinic visits.

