### 4.1 Identity of Study Treatments

DESCRIPTION OF TEST AND CONTROL PRODUCTS		
	Test Product	Control Product
LID Number	LID017569	N/A
Lens identified in randomization system as:	LID017569	Biofinity
Material	██████████	comfilcon A
Water Content	55% (Target)	48%
Base Curve (mm)	8.4 (Target)	8.6
Diameter (mm)	14.2 (Target)	14.0
Rx powers to be available in this study (D)	-1.00 to -6.00 (0.25 steps)	-1.00 to -6.00 (0.25 steps)
Packaging, Labeling, and Supply	
 
• Blister foil pack
 
• Foil label includes at a minimum: 
 
- identifier
 
- base curve
 
- diameter
 
- manufacturing protocol number
 
- packing solution
 
- power
 
- lot number
 
- expiration date
 
- content statement
 
- investigational device statement
 
 
 
	
 
• Blister foil pack
 
• Commercial foil
 
• Available in commercial boxes of ~6 lenses per box
 
• Lenses should be stored at room temperature.
 

	
 
- Sponsor information
 
- country of origin
 
• Provided in packages of approximately 20 lenses per power identified with the following at a minimum:             
 
- color coded label stating the protocol number
 
- material identifier
 
- power
 
- an investigational use only statement
 
- tracking number
 
 
 
• Lenses should be stored at room temperature.
 
	
Usage	
 
• Wear:             
 
○ Daily Wear
 
○ Bilateral
 
○ Crossover according to randomization
 
 
 
• Replacement period: Replacement lenses will not be provided to the subject. In the event a lens needs to be replaced, the subject must return to the site for a replacement lens. Until the replacement lens is obtained, the subject must store the fellow lens in the provided lens care solution and wear their habitual spectacles.
 
• Exposure: At least 8 hours per day, 5 days per week, over a 30-day period (per study lens).
 
• Lens Care: Cleaned and disinfected with RepleniSH
 
	
Control lens procurement	Each site will procure their own control lenses. Refer to the study specific MOP for detailed instructions.	

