10.	Based upon the randomized treatment sequence, have the subject insert the appropriate Lens 1 study lenses, being careful to maintain the correct OD and OS lens assignments. [REDACTED] 
 
• Keep all lidding foils of lenses used during lens fit process for study lens accountability.
 
• Follow procedures to maintain masking.
 

11.	
Evaluate the study lenses by performing the following:
 

• logMAR VA with study lenses (OD and OS, at distance)*

 
*VA w/study lenses must be 20/25 in each eye or better for subject to leave the office

13.	
Assess and record any AEs and device deficiencies reported or observed during the study visit.
 
Note: AEs and device deficiencies must be recorded for all enrolled subjects from the time of signature of informed consent including those that screen fail.

14.	
Dispense study lenses, new lens case, and lens care solution.
 
Provide the subject with written and verbal instructions on lens wear and care.

16.	
Schedule Visit 2 to take place on study Lens 1 Day <math>8 \pm 2</math> days.
 
Note: Schedule Visit 2 at a time of day that allows a minimum of 6 hours of lens wear prior to visit.
 
Remind the subject of the following:
 

• To not use any lubricating drops during lens wear

• To wear the lenses at least 5 days a week and 8 hours per day

• To wear study lenses a minimum of 6 hours on the day of their follow-up study visit

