## 6.10 Sample Size Justification

## 7 ADVERSE EVENTS AND DEVICE DEFICIENCIES

### Terms and Definitions

Adverse Event (AE)	Any untoward medical occurrence, unintended disease or injury, or untoward clinical signs (including abnormal laboratory findings) in subjects, users or other persons, whether or not related to the investigational medical device (test product). Note: For subjects, this definition includes events related to the test product, the control product, or the procedures involved. For users or other persons, this definition is restricted to events related to the test product.
Adverse Device Effect (ADE)	AE related to the use of an investigational medical device (test product) or control product. Note: This definition includes AEs resulting from insufficient or inadequate instructions for use, deployment, implantation, installation, or operation; any malfunction; and use error or intentional misuse of the test product or control product.
Anticipated Serious Adverse Device Effect (ASADE)	Serious ADE which by its nature, incidence, severity or outcome has been identified in the risk management file.
Device Deficiency	Inadequacy of a medical device with respect to its identity, quality, durability, reliability, safety, or performance. Note: This definition includes malfunctions, use errors, and inadequate labeling.
Malfunction	Failure of a medical device to meet its performance specifications or otherwise perform as intended. Performance specifications include all claims made in the labeling of the device. The intended

	performance of the device refers to the intended use for which the device is labeled or marketed.
Non-serious Adverse Event	AE that does not meet the criteria for an SAE.

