## **7.5 Follow-Up of Subjects with Adverse Events**

The Investigator is responsible for adequate and safe medical care of subjects during the study and for ensuring that appropriate medical care and relevant follow-up procedures are maintained after the study.

The Investigator should provide the Study Sponsor with any new safety information (which includes new AEs and changes to previously reported AEs) that may affect the safety evaluation of the device. For AEs that are unresolved/ ongoing at time of subject exit from study, any additional information received at follow-up should be documented in the eCRFs up to study completion (ie, database lock).

Any additional data received up to 1 month after subject discontinuation or exit must be documented and available upon the Study Sponsor's request. All complaints received after this time period will be considered and processed as spontaneous and should be communicated to the medical device's manufacturer as per local requirements.

The Investigator should also report complaints on non-Alcon products directly to the manufacturer as per the manufacturer's instructions or local regulatory requirements.

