#### **5.3.1 Adverse Events**

The applicable definition of an AE is in the study protocol. All AEs occurring from when a subject signs informed consent to when a subject exits the study will be accounted for in the reporting.

Pre-treatment AEs will be separated from treatment-emergent AEs occurring during the study period. A pre-treatment AE is an event that occurs after signing informed consent but prior to exposure to study lenses. The period for treatment-emergent AE analysis starts from exposure to study lenses until the subject completes or is discontinued from the study. Each AE will be summarized under the exposed lens based upon the event onset date/time, up until the start of the next lens in the crossover sequence.

The following tables and supportive listings will be provided:

- Incidence of All Ocular Treatment-Emergent Adverse Events
- Incidence of All Nonocular Treatment-Emergent Adverse Events
- Listing of All Ocular Treatment-Emergent Adverse Events
- Listing of All Nonocular Treatment-Emergent Adverse Events
- Listing of All Ocular Pre-Treatment Adverse Events
- Listing of All Nonocular Pre-Treatment Adverse Events

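### Does Protocol 7.3 take adverse events attributed to the dispensed lens care solution out of the study's AE tables?

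*Protocol*

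**What the plan says.** The care solution appears in four places in the protocol.

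- The synopsis lists it under Associated Materials: "multi-purpose disinfection solution (RepleniSH".
- Section 4.1 names it in the usage row that covers test and control lenses alike: "Lens Care: Cleaned and disinfected with RepleniSH".
- Section 5.1.1 has the site hand it out at Visit 1: "Dispense study lenses, new lens case, and lens care solution". Section 5.1.3 repeats this at Visit 3.
- Section 7.3 then places it among non-study marketed products: "Any AEs and device deficiencies for non-study marketed devices/products (ie, RepleniSH) will be considered and processed as spontaneous". The sentence goes on to refer to post-market vigilance procedures and to communication with the manufacturer.

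The general AE rules carry no exception for the solution. Protocol section 7 defines an AE as an untoward occurrence "whether or not related to the investigational medical device (test product". Section 7.2 says of clinically relevant changes in study parameters or questionnaires: "These clinically relevant changes will be reported regardless of causality". SAP 5.3.1 says: "All AEs occurring from when a subject signs informed consent to when a subject exits the study will be accounted for in the reporting".

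**The concern.** Two things look wrong at first. The non-study label sits oddly on a product that the protocol prescribes and the site dispenses with each pair of lenses. And spontaneous processing is normally how a sponsor handles reports that arise outside a trial, so a site might take the sentence to mean that solution-attributed events need not go on the study eCRF.

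If sites read it that way, a mild ocular symptom would enter or miss a lens's AE table according to whether the investigator blamed the lens or the solution. Investigators know which lens is being worn (Protocol 8.2). The count per lens would then rest partly on an unmasked judgement about cause, whereas SAP 5.3.1 intends allocation by onset time alone.

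**Working it through.** The question is one of reading rather than arithmetic, so the rules are set side by side.

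**1. What the disputed sentence governs.** It says how these cases are considered and processed, and that the manufacturer should be told. It does not mention the eCRF, the safety analysis set or any table, and it contains no instruction to leave an event out.

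**2. What governs recording.** Section 7.3 itself opens by collecting AEs from informed consent onward. The note at Visit 1 (5.1.1) requires AEs and device deficiencies to be recorded for every enrolled subject, screen failures included. The AE definition applies whatever the relation to the test product, and its note also takes in events related to the control product or to study procedures. Section 7.2 is likewise independent of cause.

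**3. What governs counting.** SAP 5.3.1 accounts for all AEs between consent and exit. It places each treatment-emergent AE under the lens worn at onset, until the next lens starts. Suspected cause plays no part.

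**4. Does a report to the manufacturer replace study recording?** Not in this protocol. Section 7.5 ends by asking investigators to report complaints about non-Alcon products directly to their manufacturers. The control lens is such a product, made by CooperVision, yet AEs related to it are study AEs under the section 7 definition. The two routes can run together.

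**5. Can the label be explained?** Section 4.1 identifies two study treatments, the test and the control lens, and the adverse device effect definition is tied to those two. An ancillary product that is supplied but not under evaluation can fairly be called non-study. The label describes its regulatory role, not whether subjects use it.

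**6. What is protected under either reading?** The serious and significant non-serious events listed in section 7.1 must be reported with no exception for the solution. They include corneal staining of Grade 3 or higher and symptomatic infiltrative events. Biomicroscopy grades are tabulated, and increases of one grade and of two or more grades are listed, whatever the suspected cause (Protocol 6.8, SAP 5.3.2).

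**7. Scale.** The plan gives no AE rate. Assuming a per-lens denominator between the 32 target completers and the roughly 36 planned to enroll, one subject more or fewer with an event moves a lens's incidence by:

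- 1/36 = 2.8 percentage points
- 1/32 = 3.1 percentage points

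That is true of any single event at this sample size. It measures the size of the study and says nothing about the effect of the 7.3 sentence.

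**The case for a change.** The best argument for a change is that section 7.5 uses nearly the same phrase for reports that are outside the study: "All complaints received after this time period will be considered and processed as spontaneous". Section 7.3 has no word such as also or in addition, so a site could carry that meaning back. However, the complaints in 7.5 fall outside because they arrive after the one-month window following exit. The timing excludes them, not the phrase.

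A second argument concerns device deficiencies. The examples in section 7.1 include a cloudy solution and a leaking bottle. Both lenses come in blister foil packs, so a bottle suggests the care solution. The solution example may mean the packing solution named on the test lens foil label, and the list may be generic, but this part stands to some degree: the plan does not say whether a RepleniSH deficiency belongs on the Device Deficiency eCRF. Little follows from it. If recorded, it appears in the deficiency listing as entered on the form. If not, no information about either lens's own deficiencies is lost.

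A third argument is that causality is rated only against the medical device or study procedure, so a solution-related event would have no category of its own. The eCRF fields and listing columns are not in the documents, so it cannot be concluded that such events would be unidentifiable. Nor is the investigator's attribution final: the sponsor also assesses causality and may upgrade an event from unrelated to related.

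**Conclusion.** The wording is loose, but the plan does not contradict itself and no change follows. The 7.3 sentence leaves unsaid that vigilance handling comes on top of study recording. The cause-independent rules in the protocol and SAP 5.3.1 supply that answer, and a site and analyst who follow them produce sound AE tables. An added clause would mainly restate what those rules imply.

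The consequence is small in any case. Primary effectiveness and safety are summarised descriptively, with no hypotheses and no success criterion. The same solution is used with both lenses, and nothing in the documents shows that events would be lost or that a loss would favour one lens. Any exposure is confined to AE counts for symptoms and lower-grade findings.

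This rests on one assumption: that sites apply the general recording rules to every enrolled subject, as the protocol instructs. The handling of solution deficiencies is less explicit than that of AEs, but it does not bear on the lens results.

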### **Intensity and Causality Assessments**

Where appropriate, the Investigator must assess the intensity (severity) of the AE based upon medical judgment with consideration of any subjective symptom(s), as defined below:

#### ***Intensity (Severity)***

Mild            AE is mild if the subject is aware of but can easily tolerate the sign or symptom.

Moderate        An AE is moderate if the sign or symptom results in discomfort significant enough to cause interference with the subject's usual activities.

Severe An AE is severe if the sign or symptom is incapacitating and results in the subject's inability to work or engage in their usual activities.

For every AE in the study, the Investigator must assess the causality (Related or Not Related to the medical device or study procedure). An assessment of causality will also be performed by Study Sponsor utilizing the same definitions, as shown below:

### ***Causality***

Related An AE classified as related may be either definitely related or possibly related where a direct cause and effect relationship with the medical device or study procedure has not been demonstrated, but there is a reasonable possibility that the AE was caused by the medical device or study procedure.

Not Related An AE classified as not related may either be definitely unrelated or simply unlikely to be related (ie, there are other more likely causes for the AE).

The Study Sponsor will assess the AEs and may upgrade the Investigator's assessment of seriousness and/or causality. The Study Sponsor will notify the Investigator of any AEs that are upgraded from non-serious to serious or from unrelated to related.

## **7.4 Return product analysis**

Alcon products associated with device deficiencies and/or product related AEs should be returned and must include the Complaint # which will be provided by Study Sponsor after the case is entered in the Study Sponsor's Global Product Complaint Management System. These products should be returned to the Sponsor at the end of the study, unless instructed otherwise by the Sponsor.

## **7.5 Follow-Up of Subjects with Adverse Events**

The Investigator is responsible for adequate and safe medical care of subjects during the study and for ensuring that appropriate medical care and relevant follow-up procedures are maintained after the study.

The Investigator should provide the Study Sponsor with any new safety information (which includes new AEs and changes to previously reported AEs) that may affect the safety evaluation of the device. For AEs that are unresolved/ ongoing at time of subject exit from study, any additional information received at follow-up should be documented in the eCRFs up to study completion (ie, database lock).

Any additional data received up to 1 month after subject discontinuation or exit must be documented and available upon the Study Sponsor's request. All complaints received after this time period will be considered and processed as spontaneous and should be communicated to the medical device's manufacturer as per local requirements.

The Investigator should also report complaints on non-Alcon products directly to the manufacturer as per the manufacturer's instructions or local regulatory requirements.

## **7.6 Pregnancy in the Clinical Study**

Women of childbearing potential or women who are pregnant at the time of study entry are not excluded from participation. Pregnancy should be included in the Medical History section of the eCRF when a pregnant woman enters the study or if a woman becomes pregnant during the study. Pregnancy is not reportable as an AE; however, complications may be reportable and will be decided on a case-by-case basis.

